9.1.1 Primary endpoint(s)

The Primary endpoints are:

- Changes in pain, other symptoms, functions and knee related quality of life assessed by KOOS in patients with knee OA from the first assessment throughout the observation period
- Changes in pain, others symptoms, functions and hip related quality of life assessed by HOOS in patients with hip OA from the first assessment throughout the observation period

9.1.2 Secondary endpoint(s)

The secondary endpoint(s) is/are:

- Drug utilization of Theraflex® therapy as reported by the patient to their physician
- Patient satisfaction measured with a Likert response scale (from 1-very dissatisfied to 5 – very satisfied)
- Type, frequency and length of painkiller for the symptomatic treatment of hip OR knee OA for an observation period up to 64 weeks
- Other medical/physical therapy for OA related pain (drugs/type of therapy, duration of use, dose, frequency)

9.1.3 Strengths of study design

The non-interventional study design was chosen to allow evaluation (or assessment) of current clinical practices. In contrast to clinical studies, the design of non-interventional studies (NIS) does not include randomization and "blinding", and selection of patients does not depend on the strict criteria of inclusion/exclusion. There are also limitations to this design (e.g. no possibility for comparison), but for the purpose of the objectives in this study this methodology shall provide sufficient data.

Non-interventional studies are a valuable instrument as they allow analysis samples of patients without special selection during routine clinical practice.

A prospective non-interventional study, in contrast to a retrospective one, makes it possible to plan in advance the design, procedure of gathering and processing of data, which considerably increases validity of the results.

9.2 Setting

9.2.1 Eligibility

Male and female patients from 45 to 75 of age with hip or knee osteoarthritis stage I to III.

Approximately 1100 subjects are planned to be included in the study in about 60 study centers in Russia.

9.2.2 Inclusion criteria

Inclusion criteria:

- Patients 45 to 75 years with Hip or Knee OA stage I to III
- Patient started current treatment with Theraflex® not more than 2 weeks prior to inclusion into the study
- Personally signed and dated informed consent.

9.2.3 Exclusion criteria

Exclusion criteria:

- Patients participating in an investigational program with interventions outside of routine clinical practice
- Patients with Hip or Knee OA stage 0 or stage IV
- Contraindications for use of Theraflex® in accordance with approved label (known hypersensitivity, severe chronic renal failure)
- Females who are pregnant or breastfeeding
- Patients who completed a treatment with Theraflex® or the other Symptomatic Slow-Acting drug in Osteoarthritis (SYSADOA) less than 5 months before start of the current treatment
- Patients who completed intra-articular corticosteroids treatment in the last 3 months before enrollment .
- Patients who completed hyaluronic injections and/or platelet-rich plasma (PRP) therapy of the lower limbs in the last 6 months.

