9.2.6 Representativeness

The patients included in the study should be selected only based on eligibility according to inclusion criteria. No further selection should be applied. Investigators will be asked to sample consecutive patients whenever possible to reduce selection bias.

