9.3.3.12 Prior and concomitant treatments

All treatments obtained before study start (initiated and stopped before study start) is defined as prior treatments. Prior treatments meeting the criteria listed below are considered to be relevant to the study indication have to be documented:

- Slow-acting drugs
 - Glucosamine
 - Chondroitin
 - Gialuronic acid
 - Diacerein
 - Unsaponifiable matters of avocado and soya
- Pain syndrome therapy
 - Analgesics
 - NSAID
- Topical pain therapy
 - Topical NSAID
- Intra-articulararticular injections
- Manual therapy
- Surgery
- Physiotherapy

Treatment of comorbid diseases (Diabetes mellitus, Hypertension, Obesity)

- Antihypertensive drugs
- Drugs for treatment of diabetes
- Anticoagulants
- Other

All treatments obtained in addition to Theraflex® for any indication (either initiated before study start or during the study) is defined concomitant treatments and has to be documented.

Information to be collected for medication includes:

- Trade name or INN
- Start date, stop date/ongoing
- Dose
- Unit
- Frequency
- Application route
- Indication

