Annex 3: Description of amendments

Version 1 / N/A

Amendment 1

Correction of exclusion criteria was conducted, in order to minimize the risk of including patients with different baseline level of OA treatment. At the same time it became obvious that with initial exclusion criteria slow patient recruitment is predictable.

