8.2. Protocol deviations

Protocol deviations will be presented in a listing. Protocol deviations will not result in inclusion or exclusion of subjects from analysis sets.

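### The three wash-out exclusions cover only completed therapy, so a patient still taking another slow-acting drug, or partway through an injection course, is eligible

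*Protocol*

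**What the plan says.** Protocol 9.2.3 contains three wash-out exclusions, all built on the same verb:

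- Slow-acting drugs: "Patients who completed a treatment with Theraflex® or the other Symptomatic Slow-Acting drug in Osteoarthritis (SYSADOA) less than 5 months before start" of the current Theraflex treatment.
- Corticosteroid injections: "Patients who completed intra-articular corticosteroids treatment in the last 3 months before enrollment".
- Hyaluronic acid and PRP: "Patients who completed hyaluronic injections and/or platelet-rich plasma (PRP) therapy of the lower limbs in the last 6 months". No reference date is given for this window.

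The only inclusion criterion on treatment history (9.2.2) is "Patient started current treatment with Theraflex® not more than 2 weeks prior to inclusion into the study". On the choice of patients beyond the listed criteria, 9.2.6 says "No further selection should be applied".

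On therapy already running at entry, Protocol 9.3.3.12 says "All treatments obtained in addition to Theraflex® for any indication (either initiated before study start or during the study) is defined concomitant treatments", to be documented. Annex 3 explains that the exclusion criteria were changed "in order to minimize the risk of including patients with different baseline level of OA treatment", and adds that recruitment under the initial criteria was expected to be slow. SAP 8.2 states: "Protocol deviations will not result in inclusion or exclusion of subjects from analysis sets".

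**The concern.** A wash-out rule should keep out patients whose first assessment already carries the effect of an earlier therapy. Section 7 of the protocol says that slow-acting drugs have a delayed effect that persists after they are stopped. If use that ended a few months ago justifies exclusion, use that has not ended does so at least as strongly. As worded, the rule excludes the recent past user and admits the current user.

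The primary endpoint (Protocol 9.1.1, SAP 9.1) is change in KOOS or HOOS from the first assessment, with no comparison group. Comparability of background OA treatment at Visit 1 therefore rests on the eligibility criteria. For a patient already on another slow-acting drug, or partway through an injection course, the change from Visit 1 does not describe what followed Theraflex alone.

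Such a patient also breaks no criterion. The count of eligibility violations planned in SAP 8.1 would not include them.

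**Working it through.** There is no plan figure to reproduce: Protocol 9.5 states that the study is descriptive and not powered. The check is to apply 9.2.2 and 9.2.3 literally to specific cases, then look for any other text that would change the result.

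| Patient at entry | Wash-out exclusion (9.2.3) | Theraflex start within 2 weeks (9.2.2) | Result |
|---|---|---|---|
| Another slow-acting drug finished 4 months before Theraflex | Met (4 < 5 months) | Satisfied | Excluded |
| Another slow-acting drug stopped, Theraflex begun directly after | Met (about 0 < 5 months) | Satisfied | Excluded |
| Another slow-acting drug still taken when Theraflex is added | Not met: nothing completed | Satisfied | **Admitted** |
| Corticosteroid course under way, last injection within 3 months, another due | Not met: course not completed | Satisfied | **Admitted** |
| Hyaluronic or PRP course under way | Not met: course not completed | Satisfied | **Admitted** |
| Theraflex taken continuously for more than 2 weeks | Not met | Fails | Not admitted |
| Theraflex paused for 3 weeks, restarted last week | Met if the restart is a new treatment (3 weeks < 5 months) | Fails if it is one continuing treatment | Not admitted on either consistent reading |

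Text that might close the three admitted cases:

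- **Investigator selection.** 9.2.6 allows none beyond the criteria.
- **Termination rules.** 9.1 and 9.2.7 end observation on a switch to another glucosamine/chondroitin brand, and 9.2.7.3 on a switch to another slow-acting drug. A drug already being taken alongside Theraflex is not a switch.
- **Concomitant treatment.** 9.3.3.12 requires documentation and prohibits nothing.
- **Analysis set.** SAP section 6 requires one dose and some data after the start of observation. SAP 8.2 leaves analysis sets unaffected by deviations.

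**What the SAP would show.** SAP 8.5 tabulates prior and concomitant medication by ATC subgroup. SAP 9.2 adds tables of other medication and therapy for the target joint. SAP 9.3 gives percentages receiving intra-articular glucocorticosteroids, hyaluronic acid and PRP during observation. None relates use at entry to KOOS/HOOS change. Table 7.2:1 classes a drug begun before Theraflex and still running as concomitant, but so is one begun later, so the tables do not separate the two. A bullet in SAP 8.5 limits concomitant treatment to drugs started after the first dose. Under that bullet, a drug begun earlier and continued is neither prior, concomitant nor post-treatment.

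**Size.** Within one joint group, let *p* be the share of affected patients, *d1* their mean change and *d0* the mean change of the rest. The reported mean is (1 − *p*)·*d0* + *p*·*d1*, which differs from *d0* by *p*·(*d1* − *d0*). The documents give none of *p*, *d1* or *d0*. The sign depends on *d1* − *d0*: patients already settled on a slow-acting drug may improve less, while those partway through an injection course may improve more.

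**The case against.** The strongest reply is that this is a narrow drafting gap. Investigators may well take a wash-out rule to cover ongoing use, and a single injection is completed once given, so only a course with further injections due escapes. The study is descriptive, and concomitant OA therapy is itself a secondary endpoint. Section 5 of the protocol gives recruitment as the only reason for changing the exclusions. All of this stands as a limit on weight. It does not remove the gap: the text does not say what investigators are assumed to infer, about 60 centers may read it differently, and Annex 3 does give baseline comparability as a reason.

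A reader might infer three stronger points that the documents do not support:

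- **That about a quarter of entrants are affected.** Section 7 reports that 47% of surveyed knee-OA patients used additional medicines and that more than 55% used glucosamine or chondroitin. Multiplying gives 0.47 × 0.55 = 0.26, or 284 of 1100. These are survey figures on any use. The denominator of the 55% is not stated, and neither figure is the share adding Theraflex to another slow-acting drug still being taken.
- **That long-term or restarted Theraflex users get in.** 9.2.2 or 9.2.3 catches them on any consistent reading.
- **That no planned output would reveal these patients.** The tables in SAP 8.5, 9.2 and 9.3 give partial visibility. What is missing is a link to the primary endpoint.

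**Conclusion.** The point holds on the wording. The three exclusions do not reach another slow-acting drug still being taken, or an intra-articular course still in progress, and nothing else in the protocol or SAP does. The gap goes no further than that. This assumes a literal reading of *completed*; centers that read the rule more broadly would have no such patients.

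The number affected and the size and direction of any bias cannot be derived from the documents, so the results cannot be called biased on this ground. What can be said is that the criteria as written do not secure the comparability Annex 3 names, and that the planned analysis cannot show whether this affects the KOOS/HOOS changes.

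The reference dates are a lesser matter. The slow-acting window runs back from the start of Theraflex, the corticosteroid window from enrollment, and the hyaluronic/PRP window from no stated date. The first two dates are at most 2 weeks apart.

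**What to change.** 1. **Protocol 9.2.3.** Reword the three exclusions so that they also cover therapy ongoing at entry, keeping the 5-, 3- and 6-month windows. Keep enrollment as the reference date for corticosteroids: counting back from Theraflex start would miss an injection given between that start and Visit 1, which the present wording catches. State a reference date for the hyaluronic/PRP window.

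2. **SAP 8.5.** Reconcile the bullet on concomitant treatment with Table 7.2:1, so that a drug begun before Theraflex and continued is classed as concomitant.

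3. **SAP 9.1 or 9.3.** From the recorded start and stop dates, handled by the rules of Table 7.2:1, flag FAS patients with another slow-acting drug or an intra-articular course that was ongoing at Theraflex start or Visit 1, or that ended within the stated window. The window limb also catches courses recorded as separate single injections. SAP 9.3 identifies PRP by case review from enrollment onward, so that review must reach back over the window. Report the number flagged by joint, and add one table of KOOS/HOOS change from Visit 1 without them.

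The last patient visit was planned for February 2020 and the SAP is dated July 2020. On that schedule items 2 and 3 are what can still change the report; item 1 serves the record and any later study.

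The cost is one derived flag, one repeat table and a short extension of the PRP review, with no new data collection. If the rewording were applied during recruitment, some otherwise eligible patients would be turned away.

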9.2.4 Withdrawal

In this observational study, withdrawal from the study is independent of the underlying therapy and will not affect the patient's medical care. Each patient can refuse to further participate or may withdraw from the study at any time and without giving a reason. If a patient wants to terminate the study participation, no further data will be collected. However, the patient will be asked whether she/he agrees that the data collected so far can be used. In case the patient does not agree, these data will not be used for any patient level analysis of study data. This includes safety data with the exception that data already captured in the company's safety database will be kept. However, data which are relevant for primary outcomes might be displayed on an aggregated level to assess a potential bias. In case a patient would like to withdraw the consent given earlier, s/he should inform his/her doctor and the site should document the withdrawal in the Case Report Form as well as in the patient medical records.

9.2.5 Replacement

Patients will not be replaced after drop out.

9.2.6 Representativeness

The patients included in the study should be selected only based on eligibility according to inclusion criteria. No further selection should be applied. Investigators will be asked to sample consecutive patients whenever possible to reduce selection bias.

9.2.7 Visits

The investigator documents an initial visit, follow-up visits and the end of observation/final visit for each patient in the case report form (CRF). Follow-up visits occur during routine practice, the study protocol does not define exact referral dates for those visits. The end of

observation/final visit is to be documented for a period up to 64 weeks after start of the initial treatment.

The observation period for each patient is up to 64 weeks. If patient switches to another Gl and Ch brand the observation of the patient is terminated.

9.2.7.1 Prior to inclusion

A subject can only be included in the study after he/she has purchased the product in a pharmacy. However potential patient who like to participate in the study should be included as early as possible but not later than 2 weeks after they started the treatment into the study to gain data in the beginning of the Theraflex® treatment.

Patient can be made aware about the study either by the treating physician OR by a pharmacist when a patient is purchasing Theraflex®.

Physician

At the time the physician decides to give a recommendation for Gl+Ch treatment to a patient diagnosed with hip OR knee OA and once a patient is found to be potentially eligible for inclusion, the investigator will inform the patient about the study together with the recommendation of the treatment.

The investigator must explain to the patients that he/she will make the final choice on the Gl+Ch product available on the market.

Pharmacy

Pharmacy may also be approached for the recruitment of potential study participants. At the time point a subject is purchasing Theraflex® the pharmacist may inform the subject about the potential study and if there is interest by the patient, the pharmacist would make a referral to an investigator nearby participating in the study.

9.2.7.2 Visit 1: Enrollment/Initial visit

Visit 1 is the first Visit at the physician after the subject bought the product in a pharmacy and started treatment with Theraflex®. Visit 1 must be within the first 2 weeks after start of treatment with Theraflex®.

A patient who has not been informed about the study prior to the recommendation of Gl+Ch but is currently on Theraflex® treatment within no more than for 2 weeks and meets all inclusion and none of the exclusion criteria can also be included in the study.

During the visit the investigator gives the necessary explanations about the NIS, asks the patient to read the information for the study patients and the informed consent form. If the patient gives the consent to participate in the study, the informed consent is signed both by the patient and the investigator.

During the visit the investigator conducts all examinations according to the local routine clinical practice. In addition the investigator provides to the subject the PRO questionnaire and the overall satisfaction question for completion for Visit 1. If the patient has multiple joint OA or double-sided (bilateral) Knee/Hip OA, only one «target» joint to be selected for the evaluation, where the patient experiences the most severe pain at the time of enrollment. Filling in a questionnaire, the patient needs to associate his/her responses with the "target" joint only during the entire follow-up period.

Following information will be captured in the CRF:

- Date of visit
 - day, month, year
- Date of informed consent
- Radiological Diagnosis of OA of Hip or Knee according to the Kellgren and Lawrence Criteria *
- Patient demographic data
- Gender
- Date of birth
- Race / ethnicity
- Physical Examination
- Weight (kg)
- Height (cm) (V1 only)
- Vital Signs
 - Blood Pressure
 - Body Temperature (axillary temperature)
 - Heart rate
- Lifestyle
- Alcohol and tobacco use
- Review of Theraflex® drug utilization
 - Start / End of treatment
 - Dose/frequency of treatment
- KOOS or HOOS Questionnaire (PRO)
- Patient satisfaction with Theraflex®
- Medical history
- Concomitant disease(s)
- Concomitant medication
- Concomitant non-medication therapies (e.g. physiotherapy, surgery)
- Adverse events

All examinations are performed according to the local routine institutional practice as indicated by the attending physician. PRO should be completed at the time of the visit at the physician by the patient.

9.2.7.3 Follow-up Visits I & II

Follow-up visit will be the first visit at the physician during the time frame week 16-24 (Follow-up I), week 36-44 (Follow-up II), after start of treatment with Theraflex®. If patient switches to another Symptomatic Slow-Acting drug in Osteoarthritis (SYSADOA), the observation of the patient is terminated.

During the follow-up visit the investigator conducts all examinations according to the local routine clinical practice. In addition the investigator provides to the subject the PRO

questionnaire and the overall satisfaction question for completion. The patient needs to assess the outcome of joint treatment, which was selected as the “target” at the first visit.

Following information will be captured in the CRF:

- Date of visit
 - day, month, year
- Physical Examination
- Weight (kg)
- Vital Signs
 - Blood Pressure
 - Body Temperature (axillary temperature)
 - Heart rate
- Review of Theraflex® drug utilization
 - Start / End of treatment
 - Dose/frequency of treatment
- KOOS or HOOS Questionnaire (PRO)
- Patient satisfaction with Theraflex®
- Concomitant medication
- Concomitant disease(s)
- Concomitant non- medication therapies (e.g. physiotherapy, surgery)
- Adverse events

All examinations are performed according to the local routine institutional practice as indicated by the attending physician. PRO should be completed at the time of the visit at the physician by the patient.

9.2.7.4 Final Visit / End of Observation

Final Visit / End of Observation will be the first visit at the physician’s office after an observation period up to 64 weeks after start of treatment with Theraflex®. Final visit should be performed during the time frame week 56-64

During the visit the investigator conducts all examinations according to the local routine clinical practice. In addition the investigator provides to the subject the PRO questionnaire and the overall satisfaction question for completion. The patient needs to assess the outcome of joint treatment, which was selected as the target at the first visit.

Following information will be captured in the CRF:

- Date of visit
 - day, month, year
- Physical Examination
- Weight (kg)
- Vital Signs
 - Blood Pressure
 - Body Temperature (axillary temperature)
 - Heart rate
- Review of Theraflex® drug utilization

- Start / End of treatment
- Dose/frequency of treatment
- KOOS or HOOS Questionnaire (PRO)
- Patient satisfaction with Theraflex®
- Concomitant disease(s)
- Concomitant non-medication therapies (e.g. physiotherapy, surgery)
- Adverse events

All examinations are performed according to the local routine clinical practice as indicated by the attending physician. PRO should be completed at the time of the visit at the physician by the patient.

Premature end of therapy does not automatically imply end of documentation: the patient should be followed up until the end of the observation period (64 weeks) or until no longer possible.

Table 2: Tabulated overview on variables collected during the study

	Prior to inclusion to the study	Visit 1 Inclusion into the study	Visit 2 & 3 Follow-up visit	Visit 4 Final Visit / End of Observation
		First Visit after starting treatment with Theraflex® [not more than 2 weeks]	Week 16-24 Week 36-44 after start of treatment with Theraflex®	Week 56-64 after start of treatment with Theraflex®
Assessment of inclusion / exclusion criteria		X		
Information about the study	X			
Written Informed Consent		X		
Patient demographic data		X		
Physical Examination*		X	X	X
Height /Weight**		X	X	X
Vital signs		X	X	X
OA Staging according to Kellgren & Lawrence*		X		
Lifestyle		X		
Concomitant therapies other than drug		X	X	X
Medical history /concomitant diseases		X	X	X

Concomitant medication		X	X	X
Adverse events		X	X	X
Review of Theraflex® drug utilization		X	X	X
KOOS or HOOS Questionnaire (PRO)		X	X	X
Patient satisfaction (PRO)		X	X	X

*performed in accordance with local practice

** Height at Visit 1 only

